6.3. Exploratory Objectives

The exploratory objectives of this study are to:

- Assess the effect of baseline circulating MBL levels on PK and PD measures
- Assess the effect of baseline circulating MASP-2 levels on PK and PD measures
- Describe the effect of OMS721 on TMA laboratory markers in patients with aHUS and TTP

7. STUDY DESIGN AND PROCEDURES

7.1. Summary of Study Design

This is a Phase 2, uncontrolled, three-stage, ascending-dose-escalation study in patients with TMA: aHUS, TTP, or HSCT-TMA. As originally designed, the primary outcomes to be measured were safety and clinical activity. The secondary outcomes to be measured were PK,

CONFIDENTIAL

No use, disclosure or reproduction outside of Omeros without prior written authorization

PD, and immunogenicity (i.e., presence of ADA response). Amendment 10 discontinued enrollment of patients with aHUS and TTP. Amendment 11 provides for collection of additional data from patients with HSCT-TMA, changes the primary and secondary objectives to focus on HSCT-TMA, and defines criteria by which to determine clinical response to treatment. Amendment 11 also provides for collection of PK and PD measures for analysis within integrated population PK and PD analyses across different studies.

OMS721 is to be used in conjunction with standard of care treatments. Standard of care treatments are not to be delayed or withheld from patients entering this study. These treatments should be initiated according to local standard of care. For example, plasma exchange should not be delayed while waiting for initiation of OMS721 treatment if local standard of care is to administer plasma exchange.

In Stage 1 of the study, OMS721 was administered to 3 cohorts (Cohort 1, Cohort 2, and Cohort 3), with dose escalation by cohorts to identify the optimal dosing regimen. After enrollment and treatment of each cohort, there was a safety review to determine whether dose escalation should proceed. In Stage 2, the dose selected in the first stage was administered to expanded cohorts initially planned to be 40 patients per cohort with distinct etiologies (aHUS alone in 1 cohort and TTP or HSCT-TMA in the other cohort). As of Amendment 10 of this protocol, enrollment of aHUS and TTP patients was closed. As of Amendment 11 of this protocol, enrollment in the study has been completed.

Each patient in Stage 1 received 4 weekly doses of OMS721. Prior to Amendment 10, patients in Stage 2 with aHUS received 12 weekly doses, and patients with TTP or HSCT-TMA received 4 weekly doses. Patients in Stage 2 who demonstrate improvement in TMA signs during their initial treatment period may be eligible for Stage 3, which provides continued treatment under this protocol. Patients in the aHUS cohort were eligible for an additional 12 weekly doses. Patients in the HSCT-TMA cohort may be eligible for an additional 4 weekly doses. The patient's treating Investigator and the Sponsor's medical monitor will determine eligibility for Stage 3 based upon the patient's response to therapy, safety, and tolerability prior to the last scheduled treatment visit in Stage 2 in order to determine the appropriate PK draws following that visit. (Note: patients entering Stage 3 will not undergo the Stage 2 follow-up visits.) Follow-up visits are planned to allow adequate time for ADA assessment and/or at least 6 weeks of follow-up after the last dose to allow adequate time for OMS721 elimination, whichever is longer. As of Amendment 10 of this protocol, enrollment of aHUS and TTP patients was closed. As of Amendment 11 of this protocol, enrollment in the study has been completed.

Different treatment durations for the different cohorts in Stage 2 and Stage 3 are provided because the natural history and response to treatment of each disease state is different. For example, plasma therapy for acute episodes of TTP typically is stopped when remission is achieved. Relapses occur, but generally not immediately. Also, HSCT-TMA often resolves within a few weeks of calcineurin inhibitor modification. These diseases could be effectively treated with relatively short-term treatment. On the other hand, treatment for aHUS is often chronic, and relapses are common following discontinuation of treatment. Therefore, the treatment duration for the TTP/HSCT-TMA cohort is shorter than the treatment duration of the aHUS cohort.

CONFIDENTIAL

No use, disclosure or reproduction outside of Omeros without prior written authorization

OMS721 will be administered by IV infusion. The planned enrollment is up to approximately 60 patients overall. The stages, cohorts, and treatments are provided in [Table 1](#).

Table 1: OMS721-TMA-001 Treatment Stages and Cohorts

Stage, Cohort	Number of Patients Planned	OMS721 Dose
1, Cohort 1	3	0.675 mg/kg IV weekly x 4
1, Cohort 2	3	2.0 mg/kg IV weekly x 4
1, Cohort 3	3	4.0 mg/kg IV weekly x 4
2, Cohort 4 ^a	40 (aHUS)	4.0 mg/kg IV weekly x 12
3, Cohort 4 ^a	≤ 40 (aHUS)	4.0 mg/kg IV weekly x 12
2 ^b , Cohort 5	40 (TTP ^c /HSCT-TMA)	4.0 mg/kg or 370 mg IV weekly x 4
3 ^b , Cohort 5	≤40 (TTP ^c /HSCT-TMA)	4.0 mg/kg or 370 mg IV weekly x 4

Abbreviations: aHUS = atypical hemolytic uremic syndrome; HSCT-TMA = hematopoietic stem cell transplant-thrombotic microangiopathy; IV = intravenous.

^a As of Amendment 10, Cohort 4 was closed.

^b Doses for Stage 2 and Stage 3 were determined from Stage 1 PK, PD, and safety results. After Stage 1, this was 4 mg/kg. As of Amendment 10 of this protocol, the dose for HSCT-TMA patients was 370 mg IV weekly x 4. Any patients in the middle of treatment at the time of this protocol amendment remained on their original dose.

^c As of Amendment 10 of this protocol, enrollment of TTP patients was closed.

As of Amendment 11 of this protocol, enrollment in the study has been completed.

For patients with HSCT-TMA enrolled under Amendment 10 or earlier versions of this protocol, additional data will be collected. Notification and consent of patients (or legal representatives for deceased patients) for this additional data collection are being collected according to local rules and regulations.

These additional data are outlined in this amendment in Section 19.4. These data will include supplemental data on patient demographics and baseline conditions, donor characteristics, the transplant procedure, concomitant medications, TMA-related laboratory measures, transfusions, transplant complications, and outcomes. These data will be derived from medical records from the time of transplant conditioning through the last available patient contact with the site or up to 2 years (104 weeks) after the first OMS721 dose, whichever is earlier. These data were requested by regulatory authorities because patients who have undergone HSCT typically have complicated post-transplant courses, and these additional data will allow for better understanding of OMS721 response and outcomes. As of Amendment 11, enrollment in the study has been completed, and the additional data will be collected until a predetermined data cutoff date for those patients who have not reached 2 years after first OMS721 dose.

7.1.1. Stage 1

In Stage 1, eligible patients were enrolled to sequential cohorts without regard to etiology of TMA. Dose escalation was guided by safety monitoring through at least 1 week after the last patient in the cohort had completed treatment. It may have been necessary to change the number of cohorts and dose levels based on emerging PK and PD data, which would have been

CONFIDENTIAL

[figure not shown]
No use, disclosure or reproduction outside of Omeros without prior written authorization

implemented by a protocol amendment. The safety, PK, and PD data from the first stage were reviewed to set the dose for the second stage.

As of Amendment 11 of this protocol, Stage 1 is complete.

The Stage 1 study design is illustrated in [Figure 1](#).

Figure 1: Stage 1 Study Design Schematic

The Stage 1 study schedule includes 9 visits across 3 periods:

Period 1 – Screening (Visit 1, up to 4 weeks)

Period 2 – Treatment (Visit 2 to Visit 5, 4 weeks)

Period 3 – Follow-up (Visit 6 to Visit 9, 8 weeks)

[figure not shown]
The length of time for individual patient participation in Stage 1 was approximately 12 to 16 weeks, depending on the time from screening to the first dose of OMS721 administration.

7.1.2. Stage 2 and Stage 3

aHUS Cohort

The Stage 2 and Stage 3 study designs are illustrated in [Figure 2](#) and [Figure 3](#) for the aHUS cohorts. As of Amendment 10 of this protocol, enrollment of aHUS patients was closed.

Figure 2: Stage 2 Study Design Schematic (aHUS Cohort)

The Stage 2 study schedule for the aHUS cohort (Cohort 4) includes 17 visits across 3 periods:

Period 1 – Screening (Visit 1, up to 4 weeks)

Period 2 – Treatment (Visit T-1 to Visit T-12, 12 weeks)

Period 3 (if patient does not continue to Stage 3) – Follow-up (Visit F-1 to Visit F-4, 6 weeks)

The length of time for individual aHUS patient participation in Stage 2 (if he or she did not continue to Stage 3) was approximately 18 to 22 weeks, depending on the time from screening to

[figure not shown]
CONFIDENTIAL

No use, disclosure or reproduction outside of Omeros without prior written authorization

the first dose of OMS721 administration. Follow-up visits for patients who did not continue to Stage 3 occurred on Day 85, Day 92, Day 106, and Day 120.

Patients with aHUS who completed Stage 2 treatment may have been eligible for an additional 12 weeks of treatment if the Investigator believed the patient was at risk for relapse of TMA, the patient tolerated OMS721 treatment, and the patient had no conditions that increase the risk of OMS721 treatment (e.g., serious active infection). The patient's treating Investigator and the Sponsor's medical monitor determined eligibility for Stage 3 based upon the patient's response to therapy and safety and tolerability prior to the last scheduled treatment visit in Stage 2 in order to determine the appropriate PK draws following that visit. Patients entering Stage 3 did not undergo the Follow-up visits in Stage 2.

Figure 3: Stage 3 Study Design Schematic (aHUS Cohort)

The **Stage 3** study schedule for the aHUS cohort (Cohort 4) includes 16 visits across 2 periods:

Period 2 (continued from Stage 2)-Treatment (Visit T-13 to Visit T-24, 12 weeks)

Period 3 - Follow-up (Visit F-1 to Visit F-4, 6 weeks)

[figure not shown]
The length of time for individual aHUS patient participation in Stage 3 was approximately 18 weeks and the total length of time in Stage 2 and Stage 3 was approximately 30 to 34 weeks. Follow-up visits occurred on Day 169, Day 176, Day 190, and Day 204.

The overall study was planned to take approximately 48 months to complete (from first patient visit to last patient visit).

TTP/HSCT-TMA Cohort

The Stage 2 and Stage 3 study designs are illustrated in [Figure 4](#) and [Figure 5](#) for the HSCT-TMA cohort. As of Amendment 10 of this protocol, enrollment of TTP patients was closed. As of Amendment 11 of this protocol, enrollment in the study has been completed.

Figure 4: Stage 2 Study Design Schematic (HSCT-TMA Cohort)

CONFIDENTIAL

No use, disclosure or reproduction outside of Omeros without prior written authorization

The **Stage 2** study schedule for the HSCT-TMA cohort (Cohort 5) includes 4 doses with up to 9 visits across 3 periods:

Period 1- Screening (Visit 1, up to 4 weeks)

[figure not shown]
Period 2-Treatment (Visit T-1 to Visit T-4, 4 weeks)

Period 3 (if patient does not continue to Stage 3)-Follow-up (Visit F-1 to Visit F-4, 10 weeks)

The length of time for individual HSCT-TMA patient participation in Stage 2 (if he or she does not continue to Stage 3) was approximately 14 to 18 weeks, depending on the time from screening to the first dose of OMS721 administration. Follow-up visits for patients who do not continue to Stage 3 will occur on Day 29, Day 36, Day 50, and Day 92.

Patients with HSCT-TMA who have completed the Stage 2 treatment period may be eligible for an additional 4 weeks of treatment if the Investigator believes the patient is at risk for relapse of TMA or has not responded to the initial 4 weeks of treatment, the patient tolerated OMS721 treatment, and the patient has no conditions that increase the risk of OMS721 treatment (e.g., serious active infection). The patient's treating Investigator and the Sponsor's medical monitor will determine eligibility for Stage 3 based upon the patient's response to therapy and safety and tolerability prior to the last scheduled treatment visit in Stage 2 in order to determine the appropriate PK draws following that visit. Patients entering Stage 3 will not undergo the Follow-up visits in Stage 2.

Figure 5: Stage 3 Study Design Schematic (HSCT-TMA Cohort)

The **Stage 3** study schedule for the HSCT-TMA cohort (Cohort 5) includes 8 visits across 2 periods:

Period 2 (continued from Stage 2)- Treatment (Visit T-5 to Visit T-8, 4 weeks)

Period 3 -Follow-up (Visit F-1 to Visit F-4, 6 weeks)

Follow-up visits in Stage 3 for the HSCT-TMA cohort will occur on Day 57, Day 64, Day 78, and Day 92. The length of time for individual TTP/HSCT-TMA patient participation in Stage 3 will be approximately 10 weeks, and the total length of time in Stage 2 and Stage 3 will be approximately 14 to 18 weeks.

7.2. Study Rationale

This is the first study of OMS721 in patients with TMA. In addition to evaluating safety, tolerability, PK, PD, and immunogenicity, clinical activity in patients with TMA is to be obtained. Results from nonclinical toxicity studies of OMS721, Phase 1 studies in healthy volunteers, a Phase 2 study in glomerulonephropathies, and data collected in this study as of the time of this amendment indicate that there is a positive benefit/risk ratio to conduct this study at

CONFIDENTIAL

No use, disclosure or reproduction outside of Omeros without prior written authorization

the proposed doses in patients with TMA. Patients previously enrolled thus far in this study have tolerated OMS721 well. The treatment period is being extended because the non-human primate chronic toxicity study has been completed without treatment-related adverse findings, patients previously enrolled in this study have demonstrated improvement in laboratory measures of TMA, and continued treatment has been requested. Inclusion of patients in this ongoing protocol provides for better safety and efficacy evaluation than expanded access across Investigators. The difference in treatment durations reflects the different courses of the TMA subpopulations included in this study.

[REDACTED]

[REDACTED]

[REDACTED]

[REDACTED]

[REDACTED]

[REDACTED]

[REDACTED]

[REDACTED]

[REDACTED]

[REDACTED]

[REDACTED]

CONFIDENTIAL

No use, disclosure or reproduction outside of Omeros without prior written authorization

[REDACTED]

[REDACTED]

[REDACTED]

[REDACTED]

[REDACTED]

[REDACTED]

[REDACTED]

[REDACTED]

CONFIDENTIAL

No use, disclosure or reproduction outside of Omeros without prior written authorization

7.3. Study Endpoints

7.3.1. Primary Endpoints

The co-primary endpoints are:

- Safety as assessed by adverse events (AEs), vital signs, ECGs, and clinical laboratory tests (includes patients with HSCT-TMA, aHUS, and TTP)
- For HSCT-TMA patients, response to OMS721 treatment. A responder is defined as a patient with HSCT-TMA who demonstrates improvement in laboratory TMA markers (platelet count and LDH) and clinical benefit (either improvement in organ function or reduction in transfusion burden). The specific criteria are defined as follows:
 - Improvement in laboratory TMA markers:
 - Platelet count:
 - For patients with baseline platelet count $\leq 20,000/\mu\text{L}$:
 - Tripling of baseline platelet count
and
 - Post baseline platelet count $> 30,000/\mu\text{L}$
and
 - No platelet transfusions 2 days before and on the day of the platelet count collection
 - For patients with baseline platelet count $> 20,000/\mu\text{L}$
 - Increase in platelet count $\geq 50\%$
and
 - Post baseline platelet count $> 75,000/\mu\text{L}$
and
 - No platelet transfusions 2 days before and on the day of the platelet count collection
 - and**
 - LDH:
 - $\text{LDH} < 1.5 \times \text{upper limit of normal (ULN)}$
 - and**
 - Improvement in clinical status:
 - Improvement in organ function as evidenced by any of the following:
 - Improvement in renal function:

CONFIDENTIAL

No use, disclosure or reproduction outside of Omeros without prior written authorization

- Reduction of creatinine > 40%
- or
- Creatinine < ULN and reduction of creatinine > 20%
- or
- Discontinuation of renal replacement therapy (RRT)

or

- Improvement in pulmonary function:
 - Extubation and discontinuation of ventilator support
- or
- Discontinuation of non-invasive mechanical ventilation (continuous positive pressure ventilation)

or

- Improvement in neurological function:
 - Improvement in reversible neurological conditions (e.g., cessation of seizures)
- or
- Stabilization of irreversible neurological conditions (e.g., stability of neurological deficits following stroke without further deterioration or subsequent strokes)

or

- Improvement in gastrointestinal function (gastrointestinal HSCT-TMA will require diagnosis by tissue biopsy):
 - Improvement measured by improvement in the gastrointestinal measures in the Mount Sinai Acute GVHD International Consortium (MAGIC) criteria

or

- Freedom from transfusion (no transfusions for at least 4 weeks from the last transfusion except for patients who died within 4 weeks of the last transfusion, only evaluated in patients who received transfusions within the 2 weeks prior to or on the first OMS721 dose date)

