8. SELECTION AND WITHDRAWAL OF PATIENTS

8.1. Patient Inclusion Criteria

Patients may be included in the study only if they meet all of the following criteria:

1. Competent to provide informed consent.
2. Voluntarily provide informed consent in accordance with regulations and governing ethics committee requirements prior to any procedures or evaluations performed specifically for the sole purpose of the study.
3. Are age \geq 18 years at screening (Visit 1).
4. Have a diagnosis of TMA in accordance with one of the following 3 categories:
 - As of Amendment 10 of this protocol, enrollment of aHUS patients was closed. Primary aHUS, diagnosed clinically and having ADAMTS13 activity $>$ 10% in plasma. Patients are eligible with or without a documented complement mutation or anti-complement factor H (anti-CFH) antibody. Patients are categorized according to their response to plasma therapy (plasma exchange or plasma infusion):
 - Plasma therapy-resistant aHUS patients must have all of the following:
 - Screening platelet count $<$ 150,000/ μ L despite at least 4 plasma therapy treatments prior to screening
 - Evidence of microangiopathic hemolysis (presence of schistocytes, serum LDH $>$ ULN, or haptoglobin $<$ lower limit of normal [LLN])
 - Serum creatinine $>$ ULN

CONFIDENTIAL

No use, disclosure or reproduction outside of Omeros without prior written authorization

- Chronic plasma therapy-responsive aHUS patients (plasma therapy-sensitive) must require at least once-per-week plasma therapy for 4 weeks before first dose of OMS721 with serum creatinine > ULN.
- As of Amendment 10 of this protocol, enrollment of TTP patients was closed. TTP defined as having all of the following:
 - Platelet count < 150,000/ μ L
 - Evidence of microangiopathic hemolysis (presence of schistocytes, serum LDH > ULN, or haptoglobin < LLN)
 - ADAMTS13 activity \leq 10% during the current episode of TTP or historically
- Persistent HSCT-associated TMA defined as having all of the following at least 2 weeks following modification or discontinuation of calcineurin inhibitor treatment or at least 30 days after the transplant:
 - Platelet count < 150,000/ μ L
 - Evidence of microangiopathic hemolysis (presence of schistocytes, serum LDH > ULN, or haptoglobin < LLN)
 - Renal dysfunction (doubling of serum creatinine from pre-transplant)
- 5. No clinically apparent alternative explanation for thrombocytopenia and anemia.

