13.2.1. General Considerations

All data summaries will be descriptive in nature. Summary statistics for continuous variables will include number of patients, mean, median, standard deviation, minimum, and maximum. For categorical variables, frequencies and percentages will be provided. When required for the statistical analysis of a particular variable, the baseline value will be the last recorded value prior to the administration of the first dose of study treatment. There are 2 exceptions. The baseline platelet count is defined as the average of the 2 predose values. The baseline creatinine is defined as the maximum creatinine value between the diagnosis of TMA and 4 weeks after the first dose of OMS721.

Statistical analyses will be focused on the HSCT-TMA patients and will be summarized by OMS721 dose (4.0 mg/kg, 370 mg, and both doses combined). Atypical hemolytic uremic syndrome and TTP patients will be summarized separately by OMS721 dose.

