2.5. Study Endpoint Baseline

In general, the baseline of a study endpoint is the last observation prior to the first study drug administration except for platelet count.

The baseline of a laboratory parameter will be based on the central laboratory values except for platelet count.

Platelet counts from the central laboratory are to be used in the calculation of baseline. If a central laboratory value is not available and its local laboratory value is available on the same collection date, the local laboratory value will be used. In addition, if there are at least 2 platelet count collections on the same date, the first one will be used.

Baseline platelet count is defined as the average of values obtained on different days in the week (including Day 1) prior to the first dose of OMS721. If more than 3 such values are available, then the 3 values that are most proximate to the first dose of OMS721 should be used. [Table 2](#) is an example of a baseline platelet count calculation.

Table 2: Example of Baseline Platelet Count Calculation

Study Day	Central Lab	Local Lab	Value to be used to Determine Baseline
-5	Yes	Yes	Not used
-4	Yes	Yes	Central lab
-3	No	Yes	Local lab
-2 (1 st)	No	Yes	Not used
-2 (2 nd)	Yes	No	Central lab
-2 (3 rd)	Yes	Yes	Not used

In addition, if at least 1 central laboratory value is used in the baseline calculation, the reference range of the central laboratory will be used to determine the toxicity grade according to National Cancer Institute (NCI) Common Terminology Criteria for Adverse Events (CTCAE). If the baseline value is calculated from local laboratory values only, then the reference range of the local laboratory will be used.

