 - a. The first alternative response is defined as achieving an improvement in TMA markers and an improvement in renal function as defined in Section 2.1. The number and percent of the patients achieving the first alternative response will be summarized with exact 95% CI by dose for the FAS population.
 - b. The second alternative response is defined as the same as the primary endpoint by excluding the neurological function as defined in Section 2.1. The number and percent of the patients achieving the second alternative response will be summarized with exact 95% CI by dose for the FAS population.

In addition, individual patient plots of platelet count and LDH over time will be provided.

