3.2.5. Hematopoietic Stem Cell Transplant-Associated Thrombotic Microangiopathy History

HSCT history will be summarized with descriptive statistics by dose for the safety population:

- Underlying disease
- Donor source (related or unrelated)
- Time from HSCT to Day 1
- Graft-versus-host disease (Yes or No)
- Significant infection (Yes or No)
- Refractory primary disease or primary disease relapse (Yes or No)
- Graft failure or non-engraftment (Yes or No)
- Female-to-male transplant (Yes or No)
- Multiple organ TMA involvement (Yes or No)
- Mismatched donor (Yes or No)
- Neurological findings at baseline (Yes or No)
- Renal dysfunction at baseline (Creatinine > ULN, or spot urine protein $\geq 2+$ or > 30 mg/dL; Yes or No)

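### HSCT-TMA patients can enter with creatinine already below ULN, and for an analysis baseline below ULN the second renal limb asks only for a fall of more than 20%

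*Protocol*

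**What the plan says.** **Eligibility.** Protocol 8.1, criterion 4, lists "Renal dysfunction (doubling of serum creatinine from pre-transplant") among the conditions that an HSCT-TMA patient must meet. It does not mention ULN. For aHUS, the same criterion does require creatinine above ULN.

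**Endpoint.** Protocol 7.3.1, repeated in SAP 2.1, joins three renal limbs by "or":
- "Reduction of creatinine > 40"%
- "Creatinine < ULN and reduction of creatinine > 20"%
- discontinuation of renal replacement therapy

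The second limb does not require that creatinine was ever at or above ULN. Response may occur at any time after baseline, on local or central laboratory values (Protocol 13.2.5.1, SAP 2.8.2.1). No confirmatory reading is asked for.

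**Sensitivity analysis.** The first alternative response is "achieving an improvement in TMA markers and an improvement in renal function as defined in Section 2.1", so it uses the same renal rule.

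**Baseline creatinine.** Protocol 13.2.1 takes the "maximum creatinine value between the diagnosis of TMA and 4 weeks after the first dose of OMS721". SAP 2.5 says that in general "the baseline of a study endpoint is the last observation prior to the first study drug administration except for platelet count", which leaves creatinine at its last pre-dose value.

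**Subgroup.** SAP 2.8.2.1 and 3.2.5 use a Yes/No factor, "Renal dysfunction at baseline (Creatinine > ULN, or spot urine protein" at or above a stated level).

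**The concern.** A smaller required fall is reasonable when it brings creatinine back into the normal range. It loses that justification if creatinine was in the normal range at baseline. The patient then needs half the fall asked of others and crosses no clinical boundary.

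Renal improvement can by itself supply the clinical half of the primary response, and the margins are small. With 28 patients, each one is worth 3.6 percentage points (1/28). The first alternative response, which rests on renal function alone for its clinical part, inherits the rule and so does not test it.

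**Working it through.** **1. The plan's own figures.** Clopper-Pearson limits for n = 28 reproduce the stated widths (12.3% to 38.7%) and the interval at 14/28 (30.6% to 69.4%). Under the rule that the lower limit must exceed 15%, 8/28 gives 13.2% and fails, while 9/28 gives 15.9% and passes.

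**2. Who can enter below ULN.** At an exact doubling, entry creatinine = 2 x pre-transplant. This is below ULN when pre-transplant creatinine is below 0.5 x ULN. For example, 0.4 x ULN doubles to 0.8 x ULN.

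**3. Required fall.** Because the two creatinine limbs are alternatives, a patient with analysis baseline B needs a fall of min[40%, max(20%, 1 - ULN/B)]:

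| B / ULN | Required fall |
|---|---|
| any value up to 1.25 | 20% |
| 1.4 | 28.6% |
| 1.5 | 33.3% |
| 1.667 and above | 40% |

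Every baseline below ULN sits at 20%. So do baselines from ULN to 1.25 x ULN, but those patients do cross into the normal range.

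**4. What the fall leaves.** At an exact doubling, 2.0 x 0.8 = 1.6 x pre-transplant for the 20% limb, and 2.0 x 0.6 = 1.2 x for the 40% limb.

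**5. Falls by chance (illustration).** The documents give no within-patient variability. Assumptions: no true change, one pre-dose baseline, 12 later readings, independent log-normal errors. Chance of at least one reading below the threshold:

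| Assumed CV | > 20% fall | > 40% fall |
|---|---|---|
| 5% | 1% | 0% |
| 8% | 16% | 0% |
| 10% | 30% | 0.2% |
| 15% | 54% | 6% |

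The number of readings is also assumed. Protocol 19.3 schedules 7 post-dose visits with chemistry without Stage 3 (3 treatment, 4 follow-up) and 11 with it (7 and 4). Protocol 19.5 adds daily local values around the TMA episode, as available. With lag-1 correlation of 0.7 and 12 readings, the > 20% figures at CV 10% and 15% fall to 18% and 40%.

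**6. Does the noise come from entry below ULN?** Same model, CV 10%, chance of meeting either creatinine limb:

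| True creatinine / ULN | As written | Second limb only if baseline > ULN |
|---|---|---|
| 0.8 | 30% | 1.3% |
| 0.95 | 30% | 23% |
| 1.1 | 29% | 29% |

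The chance rate is almost the same just above ULN as below it. The restriction works well below ULN, only partly near it, and not at all just above it.

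**7. Effect of the baseline definition.** Under the SAP's last pre-dose value, entry below ULN generally means an analysis baseline below ULN, and step 3 applies directly. Under the protocol's maximum, a patient who enters below ULN but peaks above 1.25 x ULN within 4 weeks after first dose needs a fall of between 20% and 40%. If a peak above 1.25 x ULN came before entry, the entry value itself already meets both parts of the second limb. For example, a peak of 1.3 and entry at 0.95 x ULN is a 27% fall (1 - 0.95/1.3) to below ULN.

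**The case against.** The strongest reply is that the gap is narrow and its effect undocumented. Nothing shows that any of the 28 patients entered below ULN. Platelet and LDH criteria must be met as well, and a patient may qualify through transfusion freedom or another organ. Step 6 shows that the chance rate comes mainly from a 20% threshold applied at any time, not from entry below ULN. All of this stands.

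It is also fair that the plan is not blind to the issue. Each response criterion is listed by patient, creatinine change is analysed as a continuous variable, confounded renal criteria can be judged non-evaluable, and the "No" level of the renal subgroup isolates patients at or below ULN without proteinuria. A reader might infer that the problem could not be detected at all; the documents do not support that. What remains true is that the first alternative response, as defined, does not test it.

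A reader might also infer that the SAP's "No" level contradicts an entry criterion under which every eligible HSCT-TMA patient has renal dysfunction. The SAP spells out its definition in the same line, so this is a matter of labelling.

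Finally, enrollment is complete and the study is open-label, so rewriting the primary endpoint now would be a change made with data in view. That argues for a sensitivity analysis and does not remove the gap.

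**Conclusion.** The point holds in a limited form. The eligibility text allows entry below ULN. For any analysis baseline below ULN, the second renal limb reduces to a fall of more than 20% at any time, compatible with creatinine at up to 1.6 x pre-transplant at an exact doubling.

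The effect on the response rate cannot be derived from the documents. The 1% to 54% chance range rests on assumed CVs, 12 readings and independent errors, and similar rates apply just above ULN. It should not be read as inflation of the primary result, nor as due to entry below ULN alone. Whether the 20% threshold applies exactly also depends on which creatinine baseline governs, and the protocol and SAP disagree on that. This merits a cheap added analysis and does not call for a redefined primary endpoint.

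**What to change.** 1. Reconcile baseline creatinine between Protocol 13.2.1 (maximum up to 4 weeks after first dose) and SAP 2.5 (last pre-dose value). The remaining steps depend on this.
2. Before interim lock, apply the second renal limb only when baseline creatinine is > ULN, with patients at or below ULN needing the > 40% limb. Do this in the first alternative response and in an added sensitivity analysis of the primary response, leaving the primary definition as it is.
3. Report how many responders depend on the second limb with a baseline at or below ULN.
4. Relabel the subgroup in SAP 2.8.2.1 and 3.2.5 as creatinine > ULN or proteinuria at baseline.

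**Cost.** No new data are needed, only SAP text and a few extra table rows. A few patients may lose the renal limb in these analyses. The required fall steps from 20% to 40% at ULN, and the 40% requirement below ULN is a choice that the documents do not themselves justify. Chance falls just above ULN are not addressed.
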